## **5.0 Safety and Adverse Events**

Although this is a low risk device, all adverse events related to such procedures should be reported by type, severity, duration, outcome, and relationship to the device or procedure in order to develop an accurate understanding of the risks and benefits of these procedures.

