## 3.0 Study Objectives

This study will be an open-label, prospective pilot study. The subjects will be 100 patients who suffer from DSO. The efficacy of photodynamic therapy for treatment of onychomycosis has been demonstrated in the literature. The purpose of the study is to establish the efficacy of the specific ToeFX device, which has shown compelling results in *in vitro* and *ex vivo* (cadaver) studies but has not been tested in patients. Specifically, we wish to:

1. Determine the safety and efficacy of ToeFX photodynamic therapy in the treatment of distal subungual onychomycosis of the toenail.
2. Determine the number of treatments required to clear the nail and to cure the fungus.
3. Finalize the treatment protocol, device design and user interface.
4. Test re-infection or recurrence of fungus post-treatment.

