## 3.1 Overview of Study

### Definition of distal subungual onychomycosis (DSO)

This type of onychomycosis is the most common clinical presentation, in which the distal nail plate is separated from the nail bed. This infection presents as nails with normal surface texture and thickness but variable “bays” of white nail that extend from the distal nail tip proximally into

the area of the nail bed. This form has been the cornerstone of antifungal drug studies. Since it generally does not involve the nail matrix, it is more amenable to improvement in clinical appearance than some other forms. In this trial only mild to moderate DSO cases will be included using the Onychomycosis Severity Index (OSI). An OSI score is obtained by multiplying the score for the area of involvement (range, 0-5) by the score for the proximity of disease to the matrix (range, 1-5).

A clinician or delegate will:

- Take representative before and after photos of nail/s prior to treatment.
- Provide a description of the treatment protocol used, including any adjunctive interventions such as topical antifungal products or debridement.
- Record occurrences and frequency of any adverse events.
- Prepare a table summarizing the percent complete responders, partial responders (which may be further stratified), and non-responders.
- Ensure that fungal species are assessed.
- Ensure that clinical presentations of onychomycosis are assessed (e.g., DSO).

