### 3.2 Study Design

Study Type:	Interventional (clinical trial)
Actual Enrollment:	100 participants
Masking:	None (Open Label)
Primary Purpose:	Treatment
Study Start Date:	Immediately upon approval by Health Canada

Arm	Intervention/treatment
Arm 1 Red light only	Core technology. Formulation and red light only. Apply photosensitizer; allow to penetrate for 15 minutes; apply red light for 15 minutes.
Arm 2 Red and blue light	Apply photosensitizer; place foot under blue light and allow to penetrate for 15 minutes. Apply red light for 15 minutes.

Arm 1 will test the core technology of the ToeFX system; this study reproduces protocols described in the literature (see ‘Previous Studies’ in Section 6.02). Arm 2 pairs the core technology with application of blue light. After application of the formulation, the nail is exposed to blue light at a wavelength of 450-470 nm and an intensity of 200 mW/cm^2. The blue light has no effect on the photosensitizer; however, several research groups have confirmed that exposure to mild blue light can have anti-inflammatory effects that would improve patient

outcomes (see ‘Previous Studies’ in Section 6.02). We will assess whether inclusion of blue light in the protocol affects the clinical outcome.

Debridement should be done prior to each treatment. Debridement should not be carried out more proximally than the most proximal margin of the dystrophic nail, as this can interfere with assessment of clear nail area attributable to the device intervention. Clinician should debride the nail and apply the photosensitizer formula and let it penetrate for 15 minutes, then if applicable apply the blue light (450-470 nm). Apply the red light (640 nm) for 15 minutes. The treatment is administered 12 times over the course of 1 year.

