### **6.1 Investigator Responsibilities**

Responsibilities of the Investigator include, but are not limited to:

1. Ensuring that all personnel assisting with the clinical trial are adequately informed and understand their trial-related duties and functions
2. Obtain informed consents of subjects.
3. Permit sponsor or designated consultant to inspect facilities and records.
4. Maintain medical histories of subjects.
5. Enroll subjects, execute the study, transcribe data from source documents to case report forms, and conduct study in accordance with protocol.
6. Submit progress reports, final reports and any adverse events to the sponsor.

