## **6.2 Sponsor Responsibilities**

ToeFX Inc. is the Sponsor of this study; responsibilities include but are not limited to:

1. Selecting qualified investigators (qualifications will be documented by curriculum vitae)
2. Providing investigators with the information necessary to conduct the investigation properly
3. Providing appropriate training to the clinical site and all study personnel, as necessary
4. Documenting training where appropriate
5. Providing the devices to qualified investigators
6. Reporting and investigating unanticipated, device-related adverse events
7. Obtaining signed Investigator Agreement for each investigator prior to their participation in the study
8. Retaining records for at least 3 years following completion of this study.

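### Section 5.0 limits detailed adverse event reporting to procedure-related events, which is inconsistent with sections 3.1 and 6.1 and leaves the attribution of other events uncheckable

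*Combined protocol and SAP*

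**What the plan says.** Four places in the combined protocol and SAP set the scope of adverse event reporting.

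- Section 5.0, the only section devoted to safety: "all adverse events related to such procedures should be reported by type, severity, duration, outcome, and relationship to the device or procedure".
- Section 3.1, in the list introduced by "A clinician or delegate will": "Record occurrences and frequency of any adverse events".
- Section 6.1, among the investigator's duties: "Submit progress reports, final reports and any adverse events to the sponsor".
- Section 6.2, among the sponsor's duties: "Reporting and investigating unanticipated, device-related adverse events".

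The first objective in section 3.0 is to "Determine the safety and efficacy of ToeFX photodynamic therapy in the treatment of distal subungual onychomycosis of the toenail". The same section says that the device "has not been tested in patients". Section 3.2 describes an open-label study with two arms and debridement before each treatment. Safety is not among the endpoints in section 1.0, and section 3.6 plans no adverse event analysis. No section says who judges relatedness, by what criteria, or when.

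**The concern.** Section 5.0 uses relatedness twice: as a condition for an event to fall under the sentence, and as one of the items to report about it. Read literally, somebody must settle the causal question before the form that records the causal judgement is required. Sections 3.1 and 6.1 contain no such condition, and nothing says which wording governs at the sites.

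What is at stake is the ability to review attribution afterwards. When a device is first used in patients, its pattern of related events is not yet known, so early judgements of relatedness are at their least secure. The usual safeguard is to describe every event and grade its relationship, so that a reaction first put down to something else can be reclassified if a pattern appears. A bare count does not allow that. With no safety endpoint and no planned safety analysis, no later step in the plan would bring the gap to light.

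**Working it through.** The plan states no adverse event rate, safety threshold or safety sample size, so there is no figure to reproduce. The check is mainly a comparison of texts.

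**Step 1: scope and content, side by side**

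| Section | Events covered | Content required |
|---|---|---|
| 3.1 | all | occurrence and frequency |
| 5.0 | related to the procedures | type, severity, duration, outcome, relationship |
| 6.1 | all | submission to the sponsor; content not specified |
| 6.2 | unanticipated and device-related | reporting and investigation by the sponsor |

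**Step 2: the least that a fully compliant site must hold**

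- Event judged related: a count (3.1), submission (6.1) and all five descriptive items (5.0).
- Event judged unrelated: a count (3.1) and submission in unspecified form (6.1). None of the five items is expressly required.

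The gap is therefore in description and causality grading, not in whether the event is known.

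**Step 3: why the gap could matter (illustration on assumed values)**

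The input from the documents is n = 100 subjects (section 3.0). Two inputs are assumed: p, the chance that a subject has an event of a given kind, and s, the share of such events judged related and so described in full. Subjects are taken as independent, with at most one such event each.

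Chance of at least one fully described event = 1 − (1 − p·s)^100.

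For p = 2%:

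- s = 1: 1 − 0.98^100 = 86.7%
- s = 0.7: 1 − 0.986^100 = 75.6%
- s = 0.5: 1 − 0.99^100 = 63.4%
- s = 0.3: 1 − 0.994^100 = 45.2%

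As s goes from 1 down to 0.3, the chance falls from 63.4% to 26.0% for p = 1%, and from 95.2% to 59.5% for p = 3%.

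**Step 4: reading a zero**

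If no events are seen in 100 subjects, the exact one-sided 95% upper limit is 1 − 0.05^(1/100) = 2.95%. If the zero refers to events judged related, the limit covers only those events and says nothing about events of all causes.

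Steps 3 and 4 show that a relatedness condition could matter at this sample size. They do not estimate its effect here, because the documents give neither p nor s.

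**The case against.** The strongest reply is that the sections do not conflict. Recording everything under section 3.1, submitting everything under section 6.1 and describing related events in detail under section 5.0 can all be done at once. Section 5.0 also lists relationship as an item to report and does not contain the word only. That item is most useful if events of differing relationship are reported, so the sentence may have been meant to cover events around the procedures, with causality graded.

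Much of this stands. A reader might infer that sites would drop every event judged unrelated and that no all-event data would exist. Sections 3.1 and 6.1 rule that out, and the mismatch is one of scope, not a strict contradiction. A reader might also infer that local reactions put down to debridement would escape. Section 3.2 makes debridement part of each treatment visit, so it is plausibly among the procedures that section 5.0 has in mind, although section 5.0 does not define them and section 3.1 lists debridement as an adjunctive intervention. Section 6.2 is a separate sponsor duty in a list stated not to be exhaustive, and it does not conflict with recording all events.

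What the reply does not remove is the result of Step 2. Following all the sections together still leaves events judged unrelated without required detail. The more generous reading of section 5.0 works only if its qualifier is disregarded, and different sites may read it differently.

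**Conclusion.** The point holds as an inconsistency of scope with a practical consequence. Detailed reporting is tied to relatedness in section 5.0 and not in sections 3.1 or 6.1, so events judged unrelated need not be described or graded and their attribution cannot be re-checked. This weakens the safety evidence that the first objective calls for.

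Its size cannot be derived from the documents. A reader might go further and infer that unmasked treating clinicians filter the safety rate, or that the blue-light arm would look safer because section 3.2 credits blue light with anti-inflammatory effects. The documents do not support either inference. No section names the person who judges relatedness, although an open-label design with site staff recording events makes site judgement plausible. No safety rate is defined. Nothing in the text shows that attribution would differ by arm or in which direction, and the allocation between arms is not stated. The conclusion rests only on the wording of the sections and on a site following that wording literally.

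**What to change.** In section 5.0, delete the qualifier that confines the sentence to events related to the procedures. All adverse events, whatever their presumed cause, would then be reported by type, severity, duration, outcome and relationship to the device or procedure, with debridement expressly included. Relationship becomes a graded attribute of each event and no longer a condition of entry. It would help to state which role does the grading.

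Add to the analysis plan a table, by arm, of the proportion of treated subjects with at least one adverse event, all-cause first and related second. Make sections 3.1, 5.0 and 6.1 consistent with this scope. Section 6.2 can stay as it is.

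The cost is a wording change, a few more adverse event entries at visits that already take place, and reported counts that will look somewhat higher. The change is best made before enrolment, since detail not collected at the time cannot be reliably recovered.

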## **6.0 Study Management**

As the study sponsor, ToeFX Inc. has the overall responsibility for the conduct of the study according to Canada's Medical Device Regulations Part 3, E6 Good Clinical Practice Consolidated Guidance, ICH, 1997), ISO 14155: Part 1 and 2, the Declaration of Helsinki, Medical Device Directive, Annex X, Health Canada, and all applicable local regulatory requirements. For this study, ToeFX Inc. will have certain direct responsibilities and will delegate other responsibilities to appropriate contract consultants. Together, ToeFX Inc. and their consultants will ensure that the study is conducted according to all applicable regulations. All personnel to participate in the conduct of this clinical trial will be qualified by training, education and/or experience to perform his or her respective tasks.

NOTE: A complete list of participating investigators will be maintained and will be available upon request.

### **6.1 Investigator Responsibilities**

Responsibilities of the Investigator include, but are not limited to:

1. Ensuring that all personnel assisting with the clinical trial are adequately informed and understand their trial-related duties and functions
2. Obtain informed consents of subjects.
3. Permit sponsor or designated consultant to inspect facilities and records.
4. Maintain medical histories of subjects.
5. Enroll subjects, execute the study, transcribe data from source documents to case report forms, and conduct study in accordance with protocol.
6. Submit progress reports, final reports and any adverse events to the sponsor.

## **6.2 Sponsor Responsibilities**

ToeFX Inc. is the Sponsor of this study; responsibilities include but are not limited to:

1. Selecting qualified investigators (qualifications will be documented by curriculum vitae)
2. Providing investigators with the information necessary to conduct the investigation properly
3. Providing appropriate training to the clinical site and all study personnel, as necessary
4. Documenting training where appropriate
5. Providing the devices to qualified investigators
6. Reporting and investigating unanticipated, device-related adverse events
7. Obtaining signed Investigator Agreement for each investigator prior to their participation in the study
8. Retaining records for at least 3 years following completion of this study.

## **6.3 Protocol Deviations**

A protocol deviation is defined as any study action taken by the clinical Investigator or site personnel in conflict with the Study Protocol. Investigators must make every effort to follow the protocol except where necessary to protect the life or physical well being of a subject in an emergency. All deviations from the protocol will be reported on the appropriate Deviations Log.

Deviations must be reported to the Sponsor within a reasonable time frame. Subject specific deviations will be reported on the Deviations Log. Non-subject specific deviations, (e.g. unauthorized use of an investigational device outside the study, etc.), will be reported to the Principal Investigator.

## **6.4 Study Review Plan**

The study will be reviewed every 30-45 days by the principal investigator and the sponsor to ensure that applicable regulations are followed. This is to ensure that each person involved in the study administration carries out the required duties.

## **6.5 Ethical Considerations**

The rights, safety and well-being of clinical investigation subjects shall be protected consistent with the ethical principles laid down in the Declaration of Helsinki. This shall be understood, observed and applied at every step in this clinical investigation.

It is expected that all parties will share in the responsibility for ethical conduct in accordance with their respective roles in the investigation. The Sponsor and the Investigator(s) shall avoid improper influence or inducement of the subject, monitor, the clinical investigator(s) or other parties participating in or contributing to the clinical investigation.

### **6.5.1 Protection of Subject Confidentiality**

At all times throughout the clinical investigation, confidentiality will be observed by all parties involved. All data shall be secured against unauthorized access. Privacy and confidentiality of information about each subject shall be preserved in study reports and in any publication. Each subject participating in this study will be assigned a unique identifier.

The Investigator will maintain a confidential subject list identifying all enrolled subjects (Enrollment Log). This list will contain the assigned subject's unique identifier and name. The Investigator bears responsibility for keeping this list confidential. This list will not be provided to the study sponsor and is only to be used at the study center.

Any source documents copied for monitoring purposes by the Sponsor will be identified by using the assigned subject's unique identifier in an effort to protect subject confidentiality.

### **6.5.2 Compensation and Study funding**

Patients will be compensated for their time, parking expenses and any other costs incurred by consequence of their participation in the trial with \$200 paid in two instalments at week 25 and week 50 of the 52-week study. The study is funded by ToeFX Inc., with in-kind support of donated time and clinic space from the principal investigator.

## **6.6 Final Report**

A final report will be completed, even if the study is prematurely terminated. At the conclusion of the trial, an abstract reporting the results may be prepared and will be presented at a major meeting(s). A manuscript may also be prepared for publication in a reputable scientific journal.

## **7.0 Study Close-out**

### **7.1 Close-out**

A close-out visit will be conducted by the Sponsor or its monitor within 45 days of receipt of the last case report form.

### **7.2 Record Storage and Retention**

The Clinical Site and the Sponsor shall retain copies of all study data and documentation for a minimum of 2 years after the last approval of a marketing application in an ICH region and until there are no pending or contemplated marketing applications in an ICH region or at least 2 years have elapsed since the formal discontinuation of clinical development. The Sponsor will notify the site of the planned marketing application and clinical development timelines with regards to record storage and retention. If the lead site investigator retires, relocates, or for other reasons

withdraws from the responsibility of keeping the study records, custody shall be transferred to a person who will accept that responsibility or to ToeFX Inc.

### **7.3 Discontinuation of Study**

ToeFX Inc. reserves the right to discontinue any study for business or ethical reasons at any time, such as but not limited to, a decision to discontinue further clinical investigations with the test article, improper conduct of the study by the investigator, inability to obtain the number of subjects required by the protocol, etc. Reimbursement for reasonable expenses will be made if such action is necessary.
